## **2.0 INVESTIGATION PLAN**

### **2.1 Study Design**

This study is a randomized single-center single-blinded placebo controlled trial of patients age 21-90 with paroxysmal atrial fibrillation. This study will be conducted at University of California, San Francisco (UCSF) Medical Center. One hundred patients will be enrolled and will receive the study infusion (alcohol or placebo infusion).

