### **2.2 Randomization and Treatment Groups**

Participants will be allocated (1:1) to a study assignment, using alternating blocked randomization (in blocks of five). Participants will be assigned to either the Ethanol Infusion group or to the Placebo Infusion group.

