### **3.2 Catheter Placement**

Following the initiation of sedation, intra-cardiac multipolar electrocatheters will be placed in the following positions under fluoroscopic guidance: decapolar catheter in the coronary sinus (CS), decapolar catheter along the crista terminalis, quadripolar catheter along the medial tricuspid annulus at the position of the His bundle, duodecapolar circular catheter in the left upper pulmonary vein, and quadripolar ablation catheter in the right upper pulmonary vein. If the ablation procedure were a cryoballoon PVI, four, instead of five, catheters will be used: decapolar catheter in the coronary sinus (CS), decapolar catheter along the crista terminalis, quadripolar catheter along the medial tricuspid annulus at the position of the His bundle, and cryoballoon catheter in the left upper pulmonary vein. (See Operations Manual for details)

Catheter repositioning should be avoided to prevent disrupting post-procedure conduction time measurements. Prior to transseptal access, the alcohol or placebo solution will be connected to minimize left atrial time.

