### 3.5 Post-Infusion EP Study

As soon as the blood alcohol content reaches a steady state of  $0.080\% \pm 0.002\%$ , a one-minute premature atrial contraction (PAC) count will be conducted. AERP measurements will then be taken at the following bipoles: CS proximal, CS distal, high right atrium (crista terminalis catheter), left upper pulmonary vein, and right upper pulmonary vein. The AERP will be obtained by an incremental technique using a 600 ms drive cycle length for 8 beats (S1) at twice pacing threshold with incremental steps for the atrial extrastimuli (S2). The first drive train at each location should begin with an atrial extrastimuli (S2) of 140 ms, which is not expected to result in atrial capture. Once the first atrial capture is achieved, the S2 will be decreased by 5 ms. AERP will be defined as the longest S1-S2 interval that fails to result in atrial capture. (See Operations Manual for details)

Following the PAC count and AERP measurements, a phenylephrine infusion will be started prior to the initiation of the isoproterenol infusion to maintain a mean arterial pressure of  $>60$  mmHg. Isoproterenol hydrochloride will then be infused at the following rates for 2 minutes each: 3 mcg/min, 6 mcg/min, 12 mcg/min, and 20 mcg/min. If AF or another arrhythmia initiates at any point during the isoproterenol infusion and is sustained over 30 seconds, the isoproterenol infusion will be stopped, the rhythm documented, and the study terminated.

If neither AF nor another arrhythmia lasting over 30 seconds occurs after 2 minutes of 20 mcg/min isoproterenol infusion, the isoproterenol infusion will be stopped. Once the heart rate falls below 100 bpm, up to 3 bursts of rapid atrial pacing will be performed from the CS proximal bipole. If AF or another arrhythmia initiates at any point during the burst pacing and is sustained over 30 seconds, the study will be terminated and the rhythm documented.

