The HOLIDAY (HOw ALcohol InDuces Atrial TachYarrhythmias) Study

NCT Number: NCT01996943

Document Type: Statistical Analysis Plan

Document Date: 12/7/2020

HOLIDAY Study Statistical Analysis

Normally distributed continuous variables are presented as means \pm SD and were compared using t-tests, and continuous variables with skewed distributions are presented as medians and interquartile ranges (IQR) and were compared using Wilcoxon rank sum or signed rank tests as appropriate. Categorical variables were compared using chi squared and Fisher's exact tests. The proportion of atrial effective refractory periods that decreased with the infusion, the proportion of conduction times that decreased with the infusion, and the continuous change in each individual atrial effective refractory period and conduction time were assessed. Linear mixed models (LMMs) to estimate average and site-specific effects on pre- to post-infusion changes in AERP and conduction times were performed, with site and baseline values modeled as fixed effects and participants as random effects; analyses were repeated after adjusting for covariates statistically significantly different between alcohol and placebo groups. Heterogeneous relationships between pulmonary vein and non-pulmonary vein sites were assessed using formal tests for interaction. In addition, given evidence of potential effect modification by biological sex (19), tests for interaction by sex on the relationships between randomization assignment and outcomes were performed. Based on a review of repeat AERP measurements in 30 AF patients at 600 ms drive cycle length prior to the trial (yielding an average ERP of 230 ms \pm 20 ms), we estimated that 22 patients in each group would provide 90% power to detect a statistically significant one standard deviation difference in the overall AERP using a single interim analysis for efficacy (assessed by an independent Data Safety Monitoring Board) and an overall two-sided $\alpha = 0.05$. We based power calculations for the secondary analysis on 25 paroxysmal AF patients in whom AF induction occurred in 20%; we therefore estimated that 50 patients in each group would provide 84% power to detect a 30% increase in AF induction (20% versus 50%) with ethanol, again using a single interim analysis for efficacy and an overall two-sided $\alpha = 0.05$. Analyses were conducted using Stata version 16 (College Station, Texas). Two-sided p values < 0.05 were considered statistically significant.

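### The SAP names participant as the only random effect, so its PV versus non-PV interaction test can reject too often unless the standard errors allow for patient-to-patient variation in that contrast

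*SAP*

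**What the plan says.** The SAP's only section uses linear mixed models to obtain both an overall effect and an effect at each site, for AERP and for conduction times. It describes the model as one "with site and baseline values modeled as fixed effects and participants as random effects". The next sentence adds: "Heterogeneous relationships between pulmonary vein and non-pulmonary vein sites were assessed using formal tests for interaction". The significance rule is "Two-sided p values < 0.05 were considered statistically significant".

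Protocol sections 3.3 and 3.5 measure AERP before and after infusion at five sites: "CS proximal, CS distal, high right atrium (crista terminalis catheter), left upper pulmonary vein, and right upper pulmonary vein". That is three non-PV and two PV sites per participant. Section 3.2 notes an exception: "If the ablation procedure were a cryoballoon PVI, four, instead of five, catheters will be used". The four catheters listed for that case include none in the right upper pulmonary vein.

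Neither document mentions a participant-by-region random effect, a residual variance structure (common or by site), a within-participant correlation structure or robust standard errors. The SAP does not say outright that the interaction test uses the mixed model. Protocol section 10 gives only t-tests or Wilcoxon tests for these outcomes and leaves the detail to the SAP.

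**The concern.** The PV versus non-PV interaction asks whether each patient's PV mean change minus non-PV mean change differs between arms. A participant intercept is common to all five sites, so it cancels out of that difference. A model with only that intercept and one residual variance then takes the standard error of the contrast from the pooled within-patient residual. This assumes that patients do not differ in how their PV tissue responds relative to the rest of the atrium. The test exists because PV tissue may behave differently, so zero is a poor value to assume for that variation.

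If patients do differ, the standard error is too small and the test rejects a true null more than 5% of the time. At stake is a mechanistic claim that ethanol acts differently in the pulmonary veins. A common residual variance would also misstate the model-based intervals for individual sites whenever PV and non-PV measurements are not equally variable.

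**Working it through.** **The plan's own figure.** For a one-SD difference at 90% power and two-sided 5%, n per group = 2 × (1.960 + 1.282)² = 21.0, rounded up to 22. Exact t-test power at 22 is 90.0% (89.6% at a final alpha of 0.048). The stated 22 per group reproduces. The plan gives no figure for the interaction test or the site-specific intervals.

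**Inputs.** Five AERP sites, 3 non-PV and 2 PV (Protocol 3.3, 3.5); 100 participants allocated 1:1, so 50 per arm (Protocol 2.1, 2.2); two-sided 5% (SAP). The documents give no variance by region, so the following are assumptions, in units of the non-PV residual variance:
- τ², the variance of a patient-level PV-specific response: 0 to 1
- k, the PV residual variance: 0.5 to 4
- participant variance: 1 (needed only for the site-specific intervals)

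**Interaction test.** The true variance of a participant's PV minus non-PV contrast is V = τ² + k/2 + 1/3. The random-intercept model uses M = s² × (1/2 + 1/3), where s² = (3 + 2k)/5 + 0.3τ². The 0.3 arises because one of the four within-participant degrees of freedom carries the region contrast. With k = 1 its expected mean square is 1 + 1.2τ², and averaging over four gives 1 + 0.3τ². The rejection rate under the null is 2[1 − Φ(1.96/√(V/M))]. Sample size cancels, so more participants would not cure the error.

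Example, τ² = 0.5 and k = 1: V = 0.5 + 0.5 + 0.333 = 1.333; M = 1.15 × 0.833 = 0.958; V/M = 1.391; 1.96/√1.391 = 1.66; rejection 9.7%.

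The simulations fitted the baseline-adjusted model by REML, with 4,000 runs per row and Monte Carlo error of about 0.3 to 0.5 points.

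| τ² | k | V | M | V/M | Closed form | Simulated | Simulated, clustered SE |
|---|---|---|---|---|---|---|---|
| 0 | 1 | 0.833 | 0.833 | 1.000 | 5.0% | 5.5% | 5.6% |
| 0.25 | 1 | 1.083 | 0.896 | 1.209 | 7.5% | 7.3% | 4.9% |
| 0.5 | 1 | 1.333 | 0.958 | 1.391 | 9.7% | 9.6% | 5.0% |
| 1 | 1 | 1.833 | 1.083 | 1.692 | 13.2% | 13.5% | 5.7% |
| 0 | 2 | 1.333 | 1.167 | 1.143 | 6.7% | 6.4% | 4.8% |
| 0 | 4 | 2.333 | 1.833 | 1.273 | 8.2% | 8.5% | 4.9% |
| 0 | 0.5 | 0.583 | 0.667 | 0.875 | 3.6% | 4.0% | 5.6% |
| 0.5 | 2 | 1.833 | 1.292 | 1.419 | 10.0% | 10.4% | 5.9% |

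For unequal residual variance alone, V/M = (3k + 2)/(2k + 3). This stays below 1.5, so the rate cannot pass about 11%. With equal numbers of PV and non-PV sites the ratio would be exactly 1.

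**Cryoballoon cases.** The documents do not give their share. If 30% of participants (assumed) lack the right upper PV site, the simulated rates are 9.4% (τ² = 0.5), 13.6% (τ² = 1), 6.3% (k = 2) and 10.3% (τ² = 0.5 with k = 2).

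Across all scenarios, clustered standard errors or the per-participant contrast gave 4.4% to 5.9%.

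**Site-specific 95% intervals.** The true variance of a single-site change is 1 + τ² + k at a PV site and 2 at a non-PV site. The model uses the average over the five sites.
- k = 2: average (3×2 + 2×3)/5 = 2.4 against 3; SE ratio √(2.4/3) = 0.894; PV coverage 92.0% (simulated 92.5%).
- k = 4: average 3.2 against 5; SE ratio 0.80; PV coverage 88.3% (simulated 88.1%).
- τ² = 0.5 and τ² = 1 with k = 1: simulated PV coverage 93.5% and 92.1%.

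Simulated non-PV coverage in these four cases is 96.1% to 98.6%, so those intervals are too wide. At k = 0.5 the pattern reverses: 96.7% for PV and 93.8% for non-PV.

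**The case against.** The strongest reply is that the SAP is a one-paragraph summary that never states a common residual variance, and that its interaction sentence stands apart from the model sentence. The analyst may have used robust standard errors or a richer structure. That is fair, and it makes the finding conditional. It does not remove it: the only structure the SAP names leaves out the variation that matters for this test, and nothing in the protocol fills the gap.

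Second, every size above rests on assumed variances. The SAP's only AERP spread, 230 ± 20 ms, is not split by region and describes the refractory period, not its change. This stands.

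Third, the SAP also assesses change at each individual site, and Protocol section 10 compares changes between arms with t-tests or rank sum tests. Those comparisons use one value per participant and need no assumption across sites. This partly protects the site-specific results but does nothing for the interaction test.

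Fourth, PV versus non-PV heterogeneity is not among the aims in Protocol section 2.5. This stands and limits the stakes.

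A reader might also arrive at rates of 9.7%, 13.2% and 17.9% for variance ratios of 0.25, 0.5 and 1.0. Those follow only if PV and non-PV sites each carry an independent patient-level effect of that size, which puts twice the variance into the contrast (2v + 5/6 in place of v + 5/6). They do not describe a single PV-specific response.

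**Conclusion.** The concern holds in conditional form. If the interaction is tested in the mixed model as described, with a common residual variance, the test can be anti-conservative: about 7.5% to 13% at a nominal 5% when the PV-specific patient variance is 0.25 to 1.0 of the residual variance. A shared PV response is the main driver. PV residual variance 2 to 4 times larger gives only about 6.5% to 8.5%, and less variable PV sites make the test conservative.

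A reader might infer that the reported interaction test and site intervals are wrong, or that any difference in PV variability inflates the error. The documents support neither: they are silent on the residual structure, they give no regional variances, and the direction depends on those variances. Nor is there evidence here against the average treatment effect or the 22 and 50 per group. The sizes are for the five-site AERP layout. The documents do not list the conduction-time measurements in the same way, so no size is claimed for those.

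**What to change.** Keep the mixed model and state its random-effect and residual structure. Base the PV interaction and the site-specific intervals on participant-clustered robust standard errors. For the interaction, an equivalent route is to compare each participant's PV minus non-PV mean change between arms, adjusted for the same contrast at baseline. A participant-level random effect for site type with region-specific residual variances is an alternative. Clustered standard errors carry over directly to conduction times; an unstructured five-site matrix does not, because the documents list five sites for AERP only.

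The SAP is written in the past tense, so the practical step is to rerun the interaction and site-specific estimates and report any change. No new data are needed. The costs are small: slightly wider intervals for the interaction, and less information from participants without both PV sites, such as cryoballoon cases.

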### Study Aims:

1. To assess the acute effects of intravenous ethanol administration on the atrial effective refractory period (AERP) and atrial conduction velocity of *in vivo* human atrial myocardium.

*Hypothesis: Intravenous administration of ethanol decreases AERP and atrial conduction velocity.*

2. To assess the acute effects of intravenous ethanol administration on the inducibility of AF of *in vivo* human atria.

*Hypothesis: Intravenous administration of ethanol increases in vivo susceptibility to AF.*

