## 2.6 Inclusion/Exclusion Criteria

### 2.6.1 Inclusion Criteria

1. Aged 21-90
2. History of paroxysmal or persistent atrial fibrillation (AF)
3. Planned procedure pulmonary vein isolation (PVI) or electrophysiology study (EPS)
4. Presenting in sinus rhythm or atrial fibrillation of recent onset (the latter confirmed by sinus rhythm documented no more than one week prior)

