### 3.4 Infusion

After the first EP study, the intravenous ethanol or placebo infusion will be initiated while the left atrial anatomic map is being constructed to reduce time added to the ablation procedure and minimize risk. The infusion is run by an iMED Gemini PC-2TX pump connected to and controlled by the CAIS 2.0 computer software. The ethanol infusion will consist of a 6% volume/volume ethanol solution in 0.45% saline titrated by the BrAC quick clamp method until a steady state is achieved at a blood alcohol concentration of 0.08%. The mean time to achieving this steady state is regulated by the CAIS 2.0 software to be approximately 20 minutes. Infusion rates are determined by the patient's height, weight, age, and sex, but are automatically adjusted depending on the patient's breath alcohol measurements, which are taken every three to four minutes until steady state is reached.

Patients assigned to the placebo group will receive 5% dextrose (D5) in 0.45% saline. BrAC measurements will be obtained at identical intervals for all participants; BrAC measurements will be randomly generated within two standard deviations of the predicted values calculated by the CAIS 2.0 software based on height, weight, age, and sex. The randomly generated BrAC values will be input into the CAIS 2.0 software, as for patients receiving an alcohol infusion, and the infusion rates will be automatically adjusted accordingly.

Once the BrAC reading is  $\pm 0.002\%$  from 0.080% (steady state), BrAC measurements will be taken every 10 minutes and input into the CAIS 2.0 software. Breath alcohol measurements will be taken using the Intoximeters Alco Sensor IV fitted with a one-way valve adaptor for intubated patients. (See Operations Manual for details)

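### Minor: the SAP's repeated adjusted analyses choose covariates by chance differences between randomised arms, and its conduction-time summary counts decreases where Aim 1 implies increases

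*SAP*

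**What the plan says.** **Adjustment.** The SAP fits linear mixed models to the pre- to post-infusion changes in AERP and conduction time, "with site and baseline values modeled as fixed effects and participants as random effects". It then states that "analyses were repeated after adjusting for covariates statistically significantly different between alcohol and placebo groups". It gives no candidate list and no other criterion for entry. Its only significance threshold is two-sided p<0.05. Protocol section 10.0 plans a logistic model for AF inducibility, adjusted for confounders that randomisation leaves unaddressed. It also gives no list and refers to the SAP for details. Allocation is 1:1 (Protocol 2.2).

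**Direction.** Among its summaries the SAP includes the proportion of AERPs that decreased and "the proportion of conduction times that decreased with the infusion". The Aim 1 hypothesis (Protocol 2.5) is: "Intravenous administration of ethanol decreases AERP and atrial conduction velocity". Protocol 3.2 asks that catheters not be repositioned, to protect the conduction-time measurements. Protocol 1.1 cites a series of 14 patients in whom whiskey lengthened atrial conduction time.

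**The concern.** In a randomised trial, a significant baseline difference says something about the draw and nothing about prognosis. Under the rule each covariate enters in about 5% of trials, whatever its link to the outcome. A strong predictor whose imbalance falls just short of p<0.05 is left out, and an irrelevant variable that crosses the line is put in. Because the candidates are not named, the adjusted model cannot be known before the baseline table is seen. Sex is an example: the SAP cites evidence that it may modify the effect and tests that interaction, yet sex enters the adjusted main-effect model only if the arms happen to differ on it. What is at stake is the precision and predictability of a supportive analysis.

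On direction, a lower velocity over a fixed path means a longer conduction time. Counting decreases fits the hypothesis for AERP and runs opposite to it for conduction time. The complement of that count merges slowing with no change, so the summary does not say how often the hypothesised effect occurred.

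**Working it through.** **The plan's own figures.** These are not in dispute.
- AERP, 1 SD difference, 90% power: n = 2(1.960 + 1.282)² / 1² = 21.0, so 22 per group. The t-test power at 22 is 90.0%. This matches the SAP.
- AF induction, 20% v 50%, 50 per group, continuity-corrected: z = [0.30 − 1/50 − 1.960·√(2·0.35·0.65/50)] / √[(0.16 + 0.25)/50] = (0.280 − 0.187)/0.0906 = 1.03. Power is 84.8%, against a stated 84%.

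**How often the rule selects anything.** For k independent candidates tested at 0.05, P(none selected) = 0.95^k. The SAP does not give k.

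| k | none selected | at least one |
|---|---|---|
| 4 | 81% | 19% |
| 10 | 60% | 40% |
| 14 | 49% | 51% |
| 30 | 21% | 79% |

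**What can stay unadjusted.** At 50 per arm the largest non-significant imbalance is t(0.975, 98)·√(2/50) = 1.984·0.200 = 0.397 SD. One covariate with R² of 0.1 or 0.2 then shifts the estimate by √R²·0.397 = 0.13 or 0.18 SD.

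**Rule against a fixed list.** Simulation assumptions: 20,000 trials per setting; four independent normal covariates, one or all four of them prognostic; total R² on the per-patient average change, after site and baseline value, of 0, 0.1 or 0.2; least squares on arm plus either the selected covariates or all four. The documents give no source for the R² values. The simulation covers the linear outcomes only, not the logistic model.

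| Setting | R² | Power, rule | Power, fixed list |
|---|---|---|---|
| 50/arm, 0.5 SD | 0 | 69.3% | 67.9% |
| | 0.1 | 69.8% | 72.4-72.5% |
| | 0.2 | 70.2-70.5% | 77.6-77.7% |
| 50/arm, 1 SD | 0.1-0.2 | 99.9% | 99.9-100% |
| 22/arm, 1 SD | 0 | 89.2% | 86.7% |
| | 0.1 | 89.6-89.7% | 89.9-90.0% |
| | 0.2 | 89.7-89.9% | 92.9% |

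The ratio of interval widths, fixed over rule, at 50 per arm is 1.015, 0.966 and 0.913 for R² of 0, 0.1 and 0.2. At 22 per arm and R² = 0 it is about 1.04. Type I error is 4.3-5.0% under the rule and 4.8-5.3% with the fixed list.

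**Direction.** Assume changes recorded to 1 ms, mean slowing of 2-3 ms and SD 3-8 ms. With a normal change rounded to 1 ms, P(decreased) = Φ((−0.5 − mean)/SD) and P(increased) = 1 − Φ((0.5 − mean)/SD).
- Mean 2, SD 3: 20% decreased, 11% unchanged, 69% increased.
- Mean 2, SD 8: 38%, 5%, 57%.
- Mean 3, SD 3: 12%, 8%, 80%.
- Mean 3, SD 8: 33%, 5%, 62%.

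The SAP's proportion gives only the first figure in each row.

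**The case against.** The strongest reply is that these are supportive analyses. The main models already carry site and baseline value, and the powered comparisons do not use the rule. That stands, and it caps the point at minor.

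The benefit of a fixed list also rests on an assumed R². At 22 per arm and 1 SD, an R² of 0.05 would make the list slightly harmful (89.6% to 88.4% power, interval about 1.4% wider). No passage shows that age, sex, AF type or planned procedure predicts the change in AERP or conduction time. Some may hardly vary: Protocol 2.1 and 2.5 describe paroxysmal AF although 2.6.1 also admits persistent AF, and section 3.0 describes the standard ablation procedure although 2.6.1 also admits an electrophysiology study. All of this stands, and the remedy has to allow for it.

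On direction, on the assumed figures only 5-11% of times are unchanged, so the share that slowed can be recovered to within that margin. The continuous changes and mixed models show slowing directly. The wording may be a drafting slip. This too stands.

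Stronger readings are tempting but not supported:
- A reader might infer that screening covariates by p-value inflates false positives. The calculation shows that it does not.
- A reader might infer that the adjusted analysis is nearly always the main model again. That holds only for few candidates; from about 14 independent ones, some covariate is selected in more than half of trials.
- A reader might infer that the proportions ignore clustering of sites within patients. The SAP names neither unit nor test for them, and site-by-site proportions, which fit the text, have no such problem.

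**Conclusion.** The point holds as a minor, inexpensive improvement. The covariate rule selects on chance imbalance, and neither document fixes the adjusted model in advance. Type I error, the main mixed models and the powered comparisons are unaffected. For four covariates with total R² of 0.1-0.2, a fixed list narrows the interval by about 3-9% at 50 per arm and adds about 3-8 points of power at 0.5 SD. At the planned 1 SD effect there is no power gain at 50 per arm and about 0-3 points at 22 per arm. Confidence is high in the reading of the text. The sizes depend on the assumed R² and number of covariates.

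The conduction-time count runs opposite to Aim 1 and no passage explains why. That longer times are expected is inferred from lower velocity over a fixed path and agrees with the earlier series cited in the protocol. The mismatch affects how one summary reads; it does not bias the two-sided tests or the continuous analyses.

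**What to change.** **Covariates.** Use one short fixed list of variables already collected, chosen on clinical grounds for expected prognostic value, whatever the baseline p-values. Age and sex are natural candidates; the infusion software already uses them ("predicted values calculated by the CAIS 2.0 software based on height, weight, age, and sex"). Add AF type or planned procedure only if they vary enough among those enrolled. Apply the list in the adjusted mixed models, on top of site and baseline value, and in the logistic model of Protocol 10.0. State the date the list was fixed. The SAP is dated 12/7/2020 and written in the past tense, so a list made now may follow sight of outcome data by arm. In that case label it post hoc and show it beside the analysis the SAP states.

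**Conduction times.** Report the proportion that increased, with unchanged and decreased shown separately, and reconcile the SAP wording with Aim 1.

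**Cost.** No new data: SAP wording and a re-run of the adjusted models. If none of four covariates is prognostic, the interval is about 1.5% wider at 50 per arm and about 4% wider at 22 per arm, where power at 1 SD falls by 2.5 points (89.2% to 86.7%). This is a reason to keep the list short.
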